4.7.5. Subgroup analyses

Analysis: The annualized incidence rate (per patient year) of rate of ‘Acute Pain Crisis’ (SCD Complications) will be performed by Pre-Oxbryta and Post-Oxbryta.

Analysis subgroups:

- Chronic pain
 - a. participants with chronic pain
 - b. participants without chronic pain
- Maximum increase from Pre-Oxbryta in Hb
 - a. Full analysis set for participants with > 1 g/dL maximum increase from Pre-Oxbryta in Hb
 - b. Full analysis set for participants with <= 1 g/dL maximum increase from Pre-Oxbryta in Hb

Analysis: Annualized incidence VOC rate for pre-Oxbryta and post-Oxbryta will be reported.

The VOC event for Pre-Oxbryta is defined as 1) SCD complication with ‘Acute Pain Crisis’ in the Pre-Oxbryta SCD complication page or 2) any qualifying complications from SCD AE prior to Treatment Start Date.

The VOC event for Post-Oxbryta is defined as any qualifying complications from SCD AE on or after the treatment start date.

The qualifying complications from SCD AE are those that met at least one of the following two conditions:

- AE preferred term (AEDECOD) to be 'Sickle cell anaemia crisis';
- type of complications (CMPTYP) is 'Acute Pain Crisis'

- 1) Analysis population: Safety analysis set where participants had a non-missing Pre-Oxbryta SCD complications will be included in the analysis.
- 2) Analysis population: Safety analysis set where participants who had a non-missing Pre-Oxbryta SCD complications or participants who had an adverse events reported in Pre-Oxbryta or Post-Oxbryta will be included in the analysis.

Analysis: The annualized VOC incidence rate (per patient year) will be performed by Pre-Oxbryta and Post-Oxbryta.

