10.3.6.1.3. Vaso-Occlusive Crises (VOCs) and Acute Chest Syndrome (ACS)

VOC data as documented in the participant's medical record will be collected and will include data on VOC events, duration, intensity, and associated interventions.

A VOC is defined as an acute episode of pain that:

- Has no medically determined cause other than a vaso-occlusive event, and
- Results in a visit to a medical facility (hospitalization, emergency department, urgent care center, outpatient clinic, or infusion center), or results in a remote contact with a healthcare provider; and
- Requires parenteral narcotic agents, parenteral nonsteroidal anti-inflammatory drugs (NSAIDs), or an increase in treatment with oral narcotics.

Data related to any events of ACS will be collected.

The events may have occurred in a medical setting (hospital, clinic, emergency room) or at home.

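### SAP 4.7.5 counts VOCs by type or preferred term on the AE form but by type alone on the pre-Oxbryta page, and applies none of the protocol's VOC criteria

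*SAP*

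**What the plan says.** Protocol section 10.3.6.1.3 gives a clinical definition. It opens "A VOC is defined as an acute episode of pain that" and lists three conditions that must all hold:

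- Cause: "Has no medically determined cause other than a vaso-occlusive event, and".
- Contact: a visit to a medical facility, "or results in a remote contact with a healthcare provider; and".
- Treatment: "Requires parenteral narcotic agents, parenteral nonsteroidal anti-inflammatory drugs (NSAIDs), or an increase in treatment with oral narcotics".

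The same section says that VOC data come from the medical record and "will include data on VOC events, duration, intensity, and associated interventions".

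SAP section 4.7.5 defines the event by how it was recorded:

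- Pre-Oxbryta, route 1: "SCD complication with ‘Acute Pain Crisis’ in the Pre-Oxbryta SCD complication page".
- Pre-Oxbryta, route 2: "any qualifying complications from SCD AE prior to Treatment Start Date".
- Post-Oxbryta: qualifying SCD AE records dated on or after treatment start, and no other source.
- Qualifying rule: "The qualifying complications from SCD AE are those that met at least one of the following two conditions". The two conditions are preferred term (AEDECOD) 'Sickle cell anaemia crisis' and type (CMPTYP) 'Acute Pain Crisis'.

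Annualized VOC rates are then reported for both periods. The SAP does not repeat the protocol's three conditions, and it does not say how the type or the term maps to them.

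**The concern.** There are two separate problems.

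First, the event counted is not the event the protocol defines, and the SAP does not say that it departs from the protocol. An entry typed as an acute pain crisis counts whether or not provider contact or the listed analgesia is shown.

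Second, the rule depends on the form. The preferred-term route applies only to SCD AE records. Post-dose events come only from that form, whereas pre-dose events come from that form and from the pre-Oxbryta page. An event that only its preferred term would identify is counted after dosing, but not if it was entered on the page before dosing.

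Protocol section 9.11.3 plans to compare event rates on treatment with those before the first dose. SAP section 4.7.3 says the limited efficacy data are there to support the benefit-risk evaluation. A counting rule that lifts the post-dose rate could look like harm or hide a benefit.

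**Working it through.** The documents give no VOC rate, event count or power figure, so there is no stated figure to reproduce. The check is a comparison of the rules, followed by an illustration with assumed shares.

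**Rules side by side**

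| Source | Period | Type counts | Term counts | Protocol criteria applied |
|---|---|---|---|---|
| Pre-Oxbryta page | Pre | Yes | No | None |
| SCD AE form | Pre | Yes | Yes | None |
| SCD AE form | Post | Yes | Yes | None |

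The only asymmetry in the stated rule is the missing term route on the first row. The missing protocol criteria affect all three rows alike.

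**Size of the form asymmetry**

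Both inputs are assumptions:

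- f: share of events identifiable only by term, taken as the same in both periods and on both forms.
- g: share of pre-dose events recorded on the SCD AE form, so that 1 − g sit on the page.

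Suppose the true rate does not change. After dosing, every event is counted. Before dosing, the term-only events on the page are lost, so the counted share is 1 − f(1 − g). The apparent post/pre ratio is therefore 1 / (1 − f(1 − g)).

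| f | g = 0 (all on the page) | g = 50% | g = 100% (none on the page) |
|---|---|---|---|
| 10% | 1/0.90 = 1.11 | 1/0.95 = 1.05 | 1.00 |
| 20% | 1/0.80 = 1.25 | 1/0.90 = 1.11 | 1.00 |
| 30% | 1/0.70 = 1.43 | 1/0.85 = 1.18 | 1.00 |

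Since f(1 − g) is never negative, the ratio is never below 1. Acting alone, the asymmetry works in one direction or not at all.

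**Effect of leaving out the protocol criteria**

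Let x be the share of counted post-dose events that fail the criteria, and y the share of counted pre-dose events that fail. The SAP ratio equals the protocol-defined ratio times (1 − y)/(1 − x).

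- x = y gives 1.00.
- x = 10%, y = 20% gives 0.80/0.90 = 0.89.
- x = 20%, y = 10% gives 0.90/0.80 = 1.125.

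Neither document gives x or y, so this effect has no known sign or size.

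**The case against.** The best defence is that the mismatch may have little effect in practice. Sites may apply the protocol definition when they choose 'Acute Pain Crisis'. The CRF completion guideline mentioned in protocol section 9.12.1 is not among the documents, so this cannot be ruled out. Neither document says it happens, however, and the preferred-term route would bypass it.

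The term rule may also serve only to recover AE-form records left without a type. Nothing shows that page entries carry a preferred term, or that any VOC on the page would be missed by type. If none would be, the current rule does no harm. This is why the table above is an illustration and not an estimate, and why both counts should be shown.

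The analysis is also descriptive. It sits under subgroup analyses, with no planned test, in a SAP written for an abbreviated report. That limits the weight of the point but does not remove the inconsistency.

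A reader might infer several stronger points that the documents do not support:

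- **That ascertainment differs, with records abstracted before dosing and home episodes added after.** Protocol sections 9.7 and 10.3.6.1.3 rest both periods on medical records. The sentence on events at home follows the one on acute chest syndrome and is not tied to a period.
- **That omitting the criteria inflates the post rate by 1/(1 − x).** As a statement about the pre/post contrast, that needs every pre-dose event to meet the criteria. The SAP omits them in both periods.
- **That VOC is the main clinical event.** No document names one. VOC is one example among several.

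**Conclusion.** The point holds as a defect in a stated counting rule. SAP 4.7.5 uses type or term on the SCD AE form and type alone on the pre-Oxbryta page, and neither count is the protocol-defined VOC. The difference lies between forms and is only partly a difference between periods, because pre-dose AE-form records can qualify by term.

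By itself the form difference can only raise the post/pre ratio or leave it at 1.00. Over the assumed term-only shares of 10% to 30%, the apparent ratio runs from 1.11 to 1.43 when all pre-dose events are on the page, from 1.05 to 1.18 when half are, and stays at 1.00 when none are. These figures assume no true change and the same term-only share in both periods and on both forms. The actual shares are not in the documents. Nothing can be said about the direction or size of the effect of omitting the protocol criteria.

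**What to change.** In SAP 4.7.5:

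1. Use one rule, type 'Acute Pain Crisis', on both forms and in both periods for the pre/post VOC rate.
2. Report the current type-or-term count as a sensitivity row.
3. State that these counts are not the VOC of protocol section 10.3.6.1.3.
4. Add a count on the protocol criteria only if contact and intervention data exist per event in both periods, with an 'unclassified' count by period. Protocol section 10.3.6.1.3 promises intervention data, but the variable list in SAP 4.3 shows no such field, and nothing confirms that the pre-Oxbryta page holds it. Data missing more often in one period would create a new imbalance.
5. Say which rule each of Tables 15.5.1 to 15.5.5 uses. Their titles refer to acute pain crisis, while the text of 4.7.5 moves between that term and VOC.

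The cost is one derivation and one or two extra rows. The downside is that type alone may miss AE-form events that were coded but not typed. In the extreme case where every pre-dose event is on the page and typed, and 10% of post-dose events are untyped, the type-only ratio would be 0.90/1.00 = 0.90 with no true change. The sensitivity row would make that visible. This is a cheap improvement.

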9.13. Strengths and Limitations of the Research Methods

A post marketing product registry enables robust and systematic data collection on product use in the real-world setting. It can also provide details on measures such as care pattern, long-term efficacy and safety which require long-term follow up and large number of patients.

Due to the observational study design, limitations include reliance on data included in participants' medical records, limited monitoring and quality control for data collection, patient population and standard of care vary among study sites, and susceptibility to multiple sources of bias for comparing outcomes.

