10.3.6.1.2. SCD Complications

For the pre Oxbryta® (Voxelotor) treatment SCD complications, all events that occurred within 12 months prior to starting Oxbryta® (Voxelotor) treatment will be recorded in the CRF.

For the post- Oxbryta® (Voxelotor) treatment SCD complications, all events occurring since the last collection timepoint will be recorded in the CRF.

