4.3. Variables

Variable	Role	Data source(s)	Operational definition
Index date	Study period	Case report form	Inform consent date
Index year	Study period	Case report form	Inform consent date
Pre-Oxbryta	Study period	Case report form	Baseline: any assessments within 12 months before receiving first dose of Oxbryta® (Voxelotor)
Post-Oxbryta	Study period	Case report form	Follow-up period for up to 5 years after the first dose of Oxbryta® (Voxelotor)
End of Treatment	Study period	Case report form	Captured from end of treatment form
End of Study	Study period	Case report form	Captured from end of study form
Age	Demographics	Case report form	Age at first dose of Oxbryta
Sex	Demographics	Case report form	Captured from the inform consent and eligibility form
Race/Ethnicity	Demographics	Case report form	Captured from the inform consent and eligibility form

SCD genotype	SCD disease history	Case report form	Captured from SCD disease history form
Hydroxyurea use	SCD disease history	Case report form	Captured from SCD disease history form
Height	Baseline characteristics	Case report form	Captured from Physical examination form
Weight	Baseline characteristics	Case report form	Captured from Physical examination form
Pre-Oxbryta SCD complications	Medical history	Case report form	Captured from Pre-Oxbryta treatment form
Concomitant Medications	Concomitant Medications	Case report form	Captured from concomitant medications form
Hemoglobin	Effectiveness endpoint measures - Hematology	Case report form	Captured from laboratory assessment-Hematology form
Reticulocyte count (%)	Effectiveness endpoint measures - Hematology	Case report form	Captured from laboratory assessment-Hematology form
Reticulocyte count (absolute)	Effectiveness endpoint measures - Hematology	Case report form	Captured from laboratory assessment-Hematology form
White blood cells (WBC)	Effectiveness endpoint measures - Hematology	Case report form	Captured from laboratory assessment-Hematology form
Aspartate Aminotransferase (AST)	Effectiveness endpoint measures - Hematology	Case report form	Captured from laboratory assessment-Hematology form
Alanine Aminotransferase (ALT)	Effectiveness endpoint measures - Hematology	Case report form	Captured from laboratory assessment-Hematology form
Bilirubin (Total)	Effectiveness endpoint measures - Chemistry	Case report form	Captured from laboratory assessment-Chemistry form

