4.7.4. Safety analysis

SCD complications are defined as 'Yes' to the question 'is this a SCD Complication' in the SCD complications/AE form while the other AEs are defined as 'No' to the question 'is this a SCD Complication' in the SCD complications/AE form.

All safety analyses will be based on safety analysis set (Section 4.2). The analysis period for Pre-Oxbryta is 12 months before the first dose of Oxbryta and the analysis period for post-Oxbryta is from the first dose of Oxbryta through end of the study or the date of dose pausing or treatment discontinuation if the date of end of study date is missing.

SAEs and protocol-specified AEs will be classified according to the Medical Dictionary for Regulatory Activities (MedDRA). The frequency of SCD complications and other AEs treatment-emergent adverse events (TEAEs) and treatment emergent SAEs will be tabulated by system organ class, preferred term, severity (and total), and relationship to Oxbryta® (Voxelotor) treatment. The pregnancy outcomes and fertility will be reported as a listing. Any events (including deaths) leading to discontinuation of the study and SAEs will be listed.

A TEAE is defined as an AE that occurs during the effective duration of treatment defined as the time from the first dose of Oxbryta through end of treatment date or the end of study completion/discontinuation date (if the date of end of treatment is missing) +28 days.

On the AE case report form there is a question “Did AE start prior to first dose?”

- If the response is “Yes” or the adverse event start date is missing, and the end date is prior to the first dose of Oxbryta, then the AE is not considered a TEAE
- If the response is “No” or “Unknown”, then the AE is considered a TEAE

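### The pre-Oxbryta crisis rate runs up to a physician-chosen first dose, so the post-Oxbryta rate can fall with no drug effect if recent crises prompted prescribing, and the SAP does not examine the run-up

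*SAP*

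**What the plan says.** SAP 4.7.5 plans annualized crisis rates for the two periods: "The annualized VOC incidence rate (per patient year) will be performed by Pre-Oxbryta and Post-Oxbryta". Tables 15.5.1 to 15.5.5 carry the results, by chronic-pain status, by maximum Hb increase, and for the safety analysis set.

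The two periods meet at first dose. SAP 4.7.4 states: "The analysis period for Pre-Oxbryta is 12 months before the first dose of Oxbryta". SAP 4.3 gives the same 12-month look-back, and Protocol 10.3.6.1.2 collects to match it: "all events that occurred within 12 months prior to starting Oxbryta® (Voxelotor) treatment will be recorded in the CRF". In SAP 4.7.5 one limb of the pre count takes "any qualifying complications from SCD AE prior to Treatment Start Date". The post count starts where that stops: "The VOC event for Post-Oxbryta is defined as any qualifying complications from SCD AE on or after the treatment start date".

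Start of treatment is left to the treating physician within usual care (Protocol 9.1.1.1 and 9.5). Neither document has a gap before first dose, a pre rate split by time, an untreated comparator, or a sensitivity analysis for the run-up. Protocol 9.13 concedes only "susceptibility to multiple sources of bias for comparing outcomes".

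**The concern.** A date chosen by a prescriber need not be a typical moment in the course of the disease. If some patients were given the drug because of a recent crisis, that crisis falls in the pre window by construction, and nothing in the post window corresponds to it. Regression to the mean then looks like benefit. This would happen even with complete histories and equal person-time weights.

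SAP 4.7.5 is the only place where the SAP sets clinical-event rates out by pre and post period; SAP 4.7.3 summarizes complication rates over the treatment period only. SAP 4.7.3 also says that the limited efficacy data are there to support the benefit-risk evaluation. Two annualized rates printed side by side in that context are likely to be read as an effect.

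**Working it through.** There is no planned figure to reproduce. SAP 4.5 has no formal sample size calculation, and neither document gives a crisis rate or a reason for prescribing.

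**Inputs.** From the documents: a 12-month pre window ending at first dose (SAP 4.3, 4.7.4), and up to 6 months from consent to first dose before a participant counts as a screen failure (SAP 4.2). Assumed: L, the true crises per patient-year, unchanged by the drug; f, the share of starts prompted by a crisis inside the window.

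**1. Size with no drug effect.** Each prompted start adds one crisis to the expected background of L in the pre year. The pre rate is therefore L+f, the post rate is L, and post/pre = L/(L+f).

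| L | f=0 | f=0.25 | f=0.5 | f=1 |
|---|---|---|---|---|
| 1 | 1.00 | 0.80 | 0.67 | 0.50 |
| 2 | 1.00 | 0.89 | 0.80 | 0.67 |
| 3 | 1.00 | 0.92 | 0.86 | 0.75 |
| 5 | 1.00 | 0.95 | 0.91 | 0.83 |

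**2. Variation between participants.** Assume gamma-distributed rates with shape 1 and mean 2, and prompted starters drawn in proportion to their rate. Their mean rate is then 4, and the cohort mean is 2(1-f)+4f = 2+2f. Post/pre = (2+2f)/(2+3f):
- f=0.25: 2.5/2.75 = 0.91
- f=0.5: 3/3.5 = 0.86
- f=1: 4/5 = 0.80

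The artefact is smaller than in the L=2 row, but still present.

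**3. What leaving out the last months does.** Drop the last c months, and let p be the share of prompting crises that lie earlier than the cut. The pre rate becomes L + f·p/((12-c)/12).

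| Timing of prompting crises | L, f | No cut | 3-month cut | 6-month cut |
|---|---|---|---|---|
| All in months -3 to 0 | 2, 0.5 | 2/2.5 = 0.80 | p=0: 1.00 | 1.00 |
| Even over months -6 to 0 | 3, 0.5 | 3/3.5 = 0.86 | p=0.5: 3/(3+0.25/0.75) = 0.90 | 1.00 |
| All in months -6 to -3 | 2, 0.5 | 2/2.5 = 0.80 | p=1: 2/(2+0.5/0.75) = 0.75 | 1.00 |

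A 3-month cut restores 1.00 only if every prompting crisis lies inside it. In the last row it makes matters worse. The 6-month interval in SAP 4.2 makes such lags possible.

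**4. The opposing bias.** If a fraction u of pre-period crises goes unrecorded, the observed pre rate is (1-u)(L+f). This equals L when u = f/(L+f): 0.5/2.5 = 20% at L=2, f=0.5, and 0.5/3.5 = 14% at L=3, f=0.5.

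**5. Precision.** For a Poisson rate the standard error scales with one over the square root of person-time. Nine months against twelve gives √(12/9) = 1.155, about 15% larger. Six months gives √(12/6) = 1.414, about 41% larger.

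**The case against.** The strongest reply is that nothing in the documents shows crises to have prompted prescribing. Protocol 9.3.1 admits anyone prescribed or already taking the drug and requires no crisis history; Protocol 7.1.2 gives Hb increase as the basis of approval. At f=0 this mechanism contributes nothing. That stands, so the point can only be conditional.

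Direction is also open. Pre-period crises are taken retrospectively from existing records, while post-period events are collected at repeated timepoints. Missed early crises would lower the pre rate and could cancel or reverse the artefact. That stands too. It is a reason to show the time course of the pre rate, because two biases of unknown size cannot be assumed to balance.

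A third reply is that the analysis is modest: descriptive rates, no ratio or test specified, tables labelled as subgroup or ad hoc, an abbreviated CSR, and a limitation already stated in Protocol 9.13. This limits the importance but does not answer the point. The protocol's Abstract and Section 9.11.3 say that on-treatment rates will be compared with those before first dose, and the stated limitation does not name regression to the mean.

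A reader might also infer that dropping the last 3 months cures the problem. The documents do not support that, since first dose may follow consent by up to 6 months and the drug may already have been prescribed at consent.

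**Conclusion.** The concern holds in conditional form. The pre window abuts a physician-chosen first dose and the plan has no means of seeing or limiting a run-up, so the pre/post crisis rates can show a fall with no drug effect. For f from 0.25 to 1 the post/pre ratio would be 0.89 to 0.67 at L=2 and 0.95 to 0.83 at L=5, and exactly 1.00 at f=0. These figures rest wholly on assumed L and f, on a constant underlying rate, and on complete recording of pre-period crises.

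The tempting stronger reading is that crises did prompt the prescriptions and that the post rate will therefore fall for an inert drug. The documents record no reason for prescribing, so they support neither step. Whether a run-up exists is something the study's own dates could help to show.

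**What to change.** In SAP 4.7.5, for Tables 15.5.1 to 15.5.5:

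- **(a)** Show the pre-Oxbryta rate by quarter (months -12 to -9, -9 to -6, -6 to -3, -3 to 0), with events and person-time in each.
- **(b)** Beside the full 12-month rate, add sensitivity pre rates for months -12 to -3 and -12 to -6, each over its own person-time. The second allows for the 6-month interval in SAP 4.2. Pre-period person-time has to be written down, because SAP 4.7 refers durations to SAP 4.7.1, which defines only the post period.
- **(c)** Report all versions, with no data-driven rule for switching between them. A raised last quarter could also reflect thinner records for the earlier months.
- **(d)** State in the CSR that the pre/post difference is open to regression to the mean, and that the benefit-risk text does not rest on the uncut 12-month comparison alone.

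The cost is SAP wording and a few table rows, with the pre-rate standard error about 15% larger over 9 months and 41% larger over 6. The change needs crisis dates on the pre-Oxbryta complication page, which is assumed here because the documents do not confirm it. Events with imputed start dates should be flagged: SAP 4.6 sets a missing day to the 15th and a missing month and day to June 15, which can put an event in the wrong quarter. A 6-month cut is not a guarantee either, since the prescription may precede consent.
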